4.2 Exclusion Criteria

Subjects are excluded from the study if any of the following exclusion criteria are met.

1. Patients with systemic or ocular diseases, or functional disorders with comorbidities, or structural abnormalities that, in the judgment of the investigator, could adversely affect the course or results of the trial (e.g. hyperthyroidism, hepatitis, acute and chronic renal insufficiency).
2. Those who have a history of allergy or serious adverse reactions to any component of IVIEW-1201 (1.0% povidone-iodine ophthalmic gel sterile solution) and Ofloxacin Eye Drops; have a history of allergy or serious adverse reactions to quinolones; or have a cumulative total of three

or more allergies to other drugs, food and environment; or who are prone to allergic symptoms such as rash and urticaria;

3. Symptoms or signs of bacterial conjunctivitis for more than 72 hours prior to screening.
4. Suspected fungal, viral or acanthamoeba infections based on clinical observations;
5. Those with severe keratitis or corneal opacity affecting the study results;
6. Active inflammation of the cornea, iris, or anterior chamber;
7. Corrected visual acuity of less than 0.2 in either eye;
8. History of eye surgery within 3 months prior to screening;
9. Those who have a history of acute or chronic dacryocystitis;
10. Those who need to wear corneal contact lenses during the trial;
11. Those who have used antibiotic eye drops or glucocorticoid eye drops within 14 days, and oral or intravenous antibiotics within 72 hours prior to screening;
12. Systemic use of steroid drugs within 14 days prior to screening. Local use of eye steroid drugs or nonsteroidal anti-inflammatory drugs (NSAIDs) within 7 days before enrollment (nasally or bronchially inhaled steroid drugs are not allowed during the study);
13. Those with co-infections requiring treatment with other anti-infective drugs in the study;
14. Those who are using other drugs that may interfere with the efficacy or safety evaluation of the drug;
15. Participation in other interventional clinical trials within 30 days prior to the study;
16. Pregnant or lactating women, women with positive pregnancy tests and those planning to become pregnant (including male subjects); subjects who do not take effective contraceptive measures within 1 month before enrollment, or subjects (including male subjects) who are unwilling to take effective contraceptive measures within the next 6 months.
17. Other conditions or illnesses judged by the clinical investigator to be unsuitable for enrollment.

4.3 Number of Cases and Allocation of Cases

There were 120 cases in total, with 60 cases in each group and 60 cases in each positive control group (ofloxacin eye drops), and they were allocated to various centers.

5. Drug Information

5.1 Investigational Drug Information

Drug Name	IVIEW-1201 (1.0% povidone-iodine ophthalmic gel sterile solution)
Specification	5g : 5mg (I2)/ bottle
Dosage Form	Eye Drops
Characteristics	It is usually a reddish brown thick liquid or gel, and after shaking it becomes a brown uniform transparent solution.
Manufacturer	Bio-Concept Laboratorie (USA)
Storage	Store in a refrigerator (2~8°C), away from light and moisture

5.2 Control Drug Information

Drug Name	Ofloxacin eye drops (Tarivid®)
Specification	5ml:15mg /bottle
Dosage Form	Eye Drops
Characteristics	Slightly yellowish green clear solution
Manufacturer	Santen Pharmaceutical (China) Co., Ltd.
Storage	Store in sealed container at 1~30°C

5.3 Package

Prior to the start of the clinical trial, all investigational drugs will be dispensed and numbered according to a randomization table. Each drug is attached with a label on its outer package. The label content includes: protocol number, drug number, blinded name of investigational drug (for clinical study use only), indication, storage, lot number, expiry date.

5.4 Study Drug Administration

IVIEW-1201

Shake well before use, 1 drop/eye/time in the affected eye. The drug shall be administered once at the study site on Day 1, and then at least once every 3 hours until bedtime, up to a maximum of 4 doses; The drug shall be administered 4 doses on Day 2, with an interval of at least 3 hours; The drug shall be administered 3 doses a day from Day 3 to Day 7, with an interval of at least 3 hours, with duration of administration of 7 days.

Ofloxacin Eye Drops (Tarivid®)

Shake well before use, 1 drop/eye/time in the affected eye. The drug shall be administered once at the study site on Day 1, and then at least once every 3 hours until bedtime, up to a maximum of 4 doses; The drug shall be administered 4 doses on Day 2, with an interval of at least 3 hours; The drug shall be administered 3 doses a day from Day 3 to Day 7, with an interval of at least 3 hours, with duration of administration of 7 days.

Administration Route

Sit or lie on back, tilt head back slightly, look up, place the test drug bottle mouth close to the eyelid of the affected eye, drop 1 drop, then gently close eyes and press the inner canthus of the eye with fingers for 1 to 2 minutes, then rest for about 5 minutes. If the test drug is not completely dropped into the eye during administration, add one drop. Among them, the test group needs to gently shake the drug solution before instilling it before use.

5.5 Prohibited Drugs or Treatments:

The Following Drugs or Treatments are Prohibited During the Study:

- Any eye medication other than the investigational drug;
- Nasally or bronchially inhaled steroid drugs;
- Systemic use of anti-infective drugs: various antibiotics, antiviral or antifungal drugs, etc., except non-facial local treatment;
- Eye hot or cold compress;
- All types of eye surgery and treatment, including physiotherapy
- Use of corneal contact lenses.

6. Process and Indicators

This study will be divided into 5 visit phases, namely Visit 1 (screening/baseline period, Day 1), Visit 2 (Day 3), Visit 3 (Day 6), Visit 4/EOT (Day 8 ±1 day) and Visit 5/EOS (Day 14±1 day).

6.1 Study Procedures/Visit 1 (screening/baseline Day 1)

- 1) Signing of Informed Consent Form.
- 2) Demographic data: including date of birth, gender, ethnicity, height, weight.

- 3) Medical history collection, including past medical history, surgical history, current medical history, co-morbidity, medication history. Any clinically significant results other than the study disease found during the screening phase should be recorded as medical history.
- 4) Vital signs (temperature, heart rate, blood pressure).
- 5) Subjective Symptoms Score
- 6) Objective Clinical Score
- 7) Best-corrected visual acuity
- 8) Corneal fluorescein staining
- 9) Slit-lamp examination.
- 10) Intraocular pressure measurement.
- 11) Collection of conjunctival sac secretion
- 12) Fundus examination.
- 13) Corneal endothelial cell count.
- 14) 12-Lead ECG.
- 15) Serum Pregnancy.
- 16) Recording of adverse events
- 17) Recording of concomitant medications
- 18) Review of diary use/instructions

Subjects who meet the inclusion criteria and do not meet the exclusion criteria should be randomized immediately. After randomization, the drug and diary card corresponding to the randomization number are dispensed to the subjects, and the subjects will be instructed to administer the drug to the affected eye while at the site, as soon as possible.

From the start of screening to the end of screening, adverse events occurring in subjects and the use of concomitant medications and treatments must be recorded in the eCRF. Subjects who fail screening are required to have basic information and the reason for failure recorded in the subject records in detail.

6.2 Study Procedures Visit 2 (D3) and Visit 3 (Day 6) (treatment period)

Subjects will return to the study site for a visit on Day 3 and Day 6 during the treatment period and complete the following:

- 1) Vital signs (temperature, heart rate, blood pressure)
- 2) Subjective Symptoms Score
- 3) Objective Clinical Score
- 4) Best-corrected visual acuity
- 5) Corneal fluorescein staining
- 6) Slit-lamp examination
- 7) Intraocular pressure measurement
- 8) Collection of conjunctival sac secretion
- 9) Check of diary card and evaluation of drug compliance
- 10) Recording of adverse events
- 11) Recording of concomitant medications

6.3 Visit 4 (D8 ± 1 day) End of Treatment

Subjects will return to the study site for a visit on Day 8±1 during the treatment period and complete the following:

- 1) Vital signs (temperature, heart rate, blood pressure)
- 2) Subjective Symptoms Score
- 3) Objective Clinical Score

- 4) Best-corrected visual acuity
- 5) Corneal fluorescein staining
- 6) Slit-lamp examination
- 7) Intraocular pressure measurement
- 8) Collection of conjunctival sac secretion
- 9) Return of investigational drug, recovery and check of diary card, and evaluation of drug compliance.
- 10) Recording of adverse events
- 11) Recording of concomitant medications

If a subject forgets to return the investigational drugs, they can be returned at Visit 5. The treatment with the investigational drug shall be terminated at the end of this visit. If the investigator determines that continued treatment is still required (IVIEW-1201 needs to be discontinued) based on the subject's symptoms and signs, the specific treatment regimen will be determined by the investigator and recorded in the eCRF. The subject will need to remain in the study until Visit 5/EOS (Day 14±1 day).

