4.Sign scoring: The three signs (conjunctival congestion, conjunctival secretion/exudation, and conjunctival edema) were scored using a 3-point scale (0 = none, 1 = mild, 2 = moderate, and 3 = severe); the researchers examined and recorded them.

5. Collection of conjunctival sac secretions: Preparation before sampling: Collect bacterial culture tubes and sterile swabs provided by the central laboratory. When sampling, fully expose the bulbar conjunctiva and fornix conjunctiva, and use a sterile swab moistened with sterile 0.9% sodium chloride solution to gently swab the surface of the conjunctival sac 4 times from the inner canthus from the inside to the outside (pay attention not to miss the inner canthus, and collect the dense secretions), avoid contact with eyelashes and eyelid margins, and use eyelid openers and other instruments when necessary. After sampling, place the specimen in a sterile transport tube, mark it, and send it to the hospital laboratory for bacterial culture. All subjects need to take secretions from both eyes for bacterial culture, and indicate the subject number and eye type.

6.Vital signs: including body temperature, heart rate, blood pressure, etc.

7.Pregnancy test: For women of childbearing age, blood/urine pregnancy test can be accepted (blood pregnancy test is the main method, if it is not met, urine pregnancy test can be selected).

8.The investigators will determine whether mydriasis is required for fundus examination. If mydriasis is required, mydriasis should be applied after secretions are collected for relevant examinations. Fundus examination or fundus photography can be accepted.

9.Medication distribution: According to the medication plan, the drugs will be distributed to the subjects. These drugs will be taken by the patients themselves or with the help of caregivers or the trial team for 7 days from D1 to D7.

10.After randomization of the subjects who meet the criteria at Visit 1, the staff of the Clinical Research Center will distribute the study drugs, and then start to instruct the subjects on the topical eye drops as soon as possible and supervise the first administration. After that, the subjects will self-administer the drugs according to the dosing regimen. On the day of Visit 2 and Visit 3, the study drugs shall not be used within 1 hour before the visit.

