10.3.3 Missing value imputation

For primary efficacy indicators, missing data are imputed using appropriate methods. If applicable, data from the last observation before dropout may be used to impute (LOCF method), and other missing value imputation methods should be explored for sensitivity analysis.

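### The Visit 4/End of Treatment window (Day 8±1) includes Day 7, a dosing day, and treatment stops at that visit, so a subject seen early on Day 7 loses 1 to 3 doses and is scored before the course is complete

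*Combined protocol and SAP*

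**What the plan says.** **Dosing.** Section 5.4 gives both arms the same schedule: one dose at the site on Day 1 and up to four in total that day, four on Day 2, and then "The drug shall be administered 3 doses a day from Day 3 to Day 7, with an interval of at least 3 hours". Footnote 9 to the study flow chart describes the course as running "for 7 days from D1 to D7".

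**Visit 4.** Section 6.3 sets the window: "Subjects will return to the study site for a visit on Day 8±1 during the treatment period". Item 9 of the visit procedures is "Return of investigational drug, recovery and check of diary card, and evaluation of drug compliance". The section then adds: "The treatment with the investigational drug shall be terminated at the end of this visit". Footnote 12 to the flow chart repeats the stop for IVIEW-1201. A subject who forgets to bring the drug back may return it at Visit 5, but that does not extend treatment.

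**Use of the visit.** Section 2.2.1 makes Visit 4 one of the two time points for the primary clinical cure rate. A conjunctival swab is also taken there for the bacterial clearance endpoint in section 2.2.2.

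**Neighbouring visits.** Section 6.2 fixes the two earlier visits: "Subjects will return to the study site for a visit on Day 3 and Day 6 during the treatment period". Neither has a window. Footnote 10 to the flow chart says: "On the day of Visit 2 and Visit 3, the study drugs shall not be used within 1 hour before the visit". Visit 4 has no such rule.

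**The concern.** The window and the dosing schedule overlap on Day 7. A site that sees a subject that day before the third dose cannot follow both sections: 5.4 requires the remaining doses, while 6.3 ends treatment. Nothing in the document bars a Day 7 visit, requires it to follow the last dose, or lets the subject finish the course afterwards.

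Two things are at stake. The subject receives a shortened course. The score and swab labelled End of Treatment are then taken while the course is still incomplete, possibly soon after a drop, and are pooled with scores from Days 8 and 9 that follow the whole course. In addition, section 6.3 lets the investigator choose another treatment at Visit 4, so an early attender could be switched before finishing the assigned one.

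**Working it through.** The plan gives no figure of its own here, so this is calendar and dose-count arithmetic.

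**Inputs**
- Visit 4 window: Day 8 ± 1 (section 6.3).
- Doses: 1 to 4 on Day 1, 4 on Day 2, 3 a day on Days 3 to 7, at least 3 hours apart (section 5.4).
- Limit for poor compliance: below 80% of the theoretical number of doses (section 8).

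**Step 1: overlap.** 8 − 1 = 7, so Visit 4 may fall on Day 7, 8 or 9. Day 7 is the last of the five three-dose days.

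**Step 2: length of the course.** Minimum 1 + 4 + 3 × 5 = 20 doses. Maximum 4 + 4 + 3 × 5 = 23 doses.

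**Step 3: earliest completion on Day 7.** Three doses have two intervals between them: 2 × 3 h = 6 h after the first dose.

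**Step 4: doses lost at a Day 7 visit.** Loss = 3 − Day 7 doses already taken. The table gives the smallest possible loss for each visit time. Compliance is (scheduled − lost) / scheduled.

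| Visit time relative to first Day 7 dose | Least loss | Share of 23 to 20 doses | Compliance (20 / 23 doses scheduled) |
|---|---|---|---|
| Before it | 3 | 3/23 = 13.0% to 3/20 = 15.0% | 17/20 = 85.0% / 20/23 = 87.0% |
| 0 to under 3 h after | 2 | 2/23 = 8.7% to 2/20 = 10.0% | 18/20 = 90.0% / 21/23 = 91.3% |
| 3 to under 6 h after | 1 | 1/23 = 4.3% to 1/20 = 5.0% | 19/20 = 95.0% / 22/23 = 95.7% |
| 6 h or more after | 0 | 0% | 100% |

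The compliance column assumes no other missed dose and the full course as denominator. Section 8 does not say whether the theoretical number runs to the end of the course or only to the visit. If it runs only to the visit, there may be no recorded shortfall at all.

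**Step 5: other visit days.** A visit on Day 8 or 9 costs no doses. Visit 5 is on Day 13 at the earliest (14 − 1), after planned dosing has ended for eyes treated from Day 1.

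**The case against.** The strongest reply is that this is loose drafting with little effect.

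- **Few subjects are likely to be affected.** With Visit 3 fixed on Day 6, a Day 7 Visit 4 would mean full examinations on consecutive days. This stands. The documents give no expected attendance by day, so *uncommon* is a judgement.
- **The plan tolerates a loss of this size.** Even three lost doses leave 85.0%, above the 80% limit. This stands too: the compliance rule works as written and is not itself defective.
- **Visit 4 was evidently meant to follow dosing.** The flow chart marks study drug administration at Visits 1, 2 and 3 but not at Visit 4, and the 1-hour rule names only Visits 2 and 3. This is good evidence of intent. It does not stop a Day 7 visit from being within the window, and it supports opening the window on Day 8.
- **Changing the window alone is not enough.** A subject who still comes on Day 7 would lose the same doses under the unchanged stop sentence. This is correct, and it is why section 6.3 also needs amending.

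A reader might infer that every Day 7 attender is undertreated, or that the cure rate or the comparison between arms is biased. The documents support neither. A visit 6 hours or more after the first dose can follow all three. The window and schedule are the same in both arms, and nothing indicates that early attendance would differ between them.

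**Conclusion.** The conflict is real and follows from the text alone. A subject seen on Day 7 less than 6 hours after that day's first dose, or before it, loses 1 to 3 of 20 to 23 doses, at most 13.0% to 15.0% of the course. One of the two primary time points is then scored before the course is complete.

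The point is minor. The share of subjects seen on Day 7 is not given and is probably small, no direction of bias between arms follows, and the effect on the cure rate cannot be quantified. Confidence is high in the overlap and the dose counts; no consequence for the result has been shown. It is worth correcting because the change is cheap and makes the End of Treatment visit what its label and the flow chart imply.

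**What to change.** 1. Change the Visit 4 window to Day 8 +1 day (Day 8 to Day 9) wherever it appears: the contents line, the synopsis rows on visits and efficacy evaluation, the flow chart, sections 2.2.1, 3.1, the opening of 6, 6.3 and 7.1.
2. Replace the stop sentence in section 6.3 with wording such as: *For eyes treated from Day 1, study drug ends after the last scheduled dose on Day 7. A subject who attends Visit 4 before that dose keeps the drug, completes the Day 7 doses and returns the drug afterwards.* Align footnote 12 of the flow chart.

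Both changes are needed. The first places the score and swab after the course; the second protects the doses of anyone who still comes early. Letting early attenders finish their doses, without moving the window, would restore the treatment but leave the score taken before the course is complete.

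The cost is one repeated window edit, one rewritten sentence with its footnote, and one day less flexibility in scheduling. A few more visits may fall out of window; these should be analysed as observed.

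Two additions are optional, since they answer no defect in the current text: a sentence in section 10.3.3 that an observed out-of-window Visit 4 score is not replaced by the Day 6 score through last observation carried forward, and a descriptive table of actual Visit 4 day by arm, with no one excluded on that basis.

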6.4 End of Study period: Visit 5 (D14 ± 1) End of Study

Subjects will complete the following:

- 1) Vital signs (temperature, heart rate, blood pressure)
- 2) Subjective Symptoms Score
- 3) Objective Clinical Score
- 4) Best-corrected visual acuity
- 5) Corneal fluorescein staining
- 6) Slit-lamp examination
- 7) Intraocular pressure measurement
- 8) Fundus examination
- 9) Corneal endothelial cell count
- 10) Serum Pregnancy
- 11) Recording of adverse events
- 12) Recording of concomitant medications

Subjects who have not returned the investigational drugs at Visit 4 should return the investigational drugs. Subjects who withdraw early should complete the last visit in accordance with the various tests, if possible.

See Appendix 1: Symptom Scoring Criteria and Appendix 2: Evaluation criteria of comprehensive efficacy for the specific criteria for scoring the symptoms and signs mentioned above.

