
Efficacy Evaluation
	
Primary outcomes
 
Clinical cure rate: The proportion of subjects with a score of 0 (on a 3-point scale) for bulbar conjunctival congestion and 0 (on a 3-point scale) for conjunctival secretion/exudation at Visit 4 (Day 8±1 day) and Visit 5 (Day 14±1 day).
 
Secondary outcomes
 
Clearance rate: The clearance rate of each major pathogenic bacteria at Visit 2, 3, 4 and 5: Stratified analysis shall be conducted according to the type of pathogenic bacteria and the visit time point, and the clearance rate of each kind of bacteria by the investigational drug at different times shall be calculated. Bacterial clearance is defined as positive bacterial culture at baseline and negative bacterial culture at the last visit. Bacterial clearance rate = (number of subjects cleared + number of subjects assumed to be cleared) / total number of subjects enrolled × 100%.
 
Exploratory outcomes
 
Mean clinical improvement rate at Visit 2, 3, 4 and 5:
 
Clinical improvement rate = (pre-treatment score - post-treatment score) / pre-treatment score x

	
100%. The score of symptoms and signs is the sum of the scores for pain, foreign body sensation, photophobia, tearing, conjunctival congestion, conjunctival secretion/exudation and conjunctival edema.
 
Total effective rate (%) at Visit 2, 3, 4 and 5:
 
Total effective rate (%) = (number of subjects cured+ number of subjects markedly effective) / total number of subjects available for evaluation of efficacy $\times 100\%$. Comprehensive efficacy evaluation: defined as cured, markedly effective, effective and ineffective; Calculate the total effective rate; See Appendix 2 for judgment criteria.

Safety Evaluation	
Including adverse events/serious adverse events, clinically significant changes in ocular and systemic symptoms and signs before and after treatment.

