	
Safety analysis
 
Adverse event: Treatment-Emergent Adverse Event (TEAEs) should be focused on, i.e. treatment-emergent adverse events. The χ^2 test or Fisher's exact probability method is used to compare the incidence of adverse events in each group and the incidence of adverse events related to the study drug. All adverse events will be coded using the Medical Dictionary for Regulatory Activities (MedDRA) and the number of cases, incidence and frequency of each type of adverse event occurring during the trial will be summarized by SOC/PT. The adverse events occurring in this trial will be tabulated and described.

--	---

Overview of study flow chart of IVIEW 1201

Visit schedule	Visit 1	Visit 2	Visit 3	Visit 4/ EOT	Visit 5/ EOS
Test stage	Screening/Baseline/Day 1	Day 3	Day 6	Day 8	Day 14/ Early withdrawal
Visit window period				(± 1 days)	(± 1 days)
Signing of Informed Consent Form	X				
Inclusion and exclusion criteria	X				
Randomization	X				
Demographic data ¹	X				
History taking ²	X				
Subjective Symptoms Score ³	X	X	X	X	X
Objective Clinical Score ⁴	X	X	X	X	X
Collection of conjunctival sac secretion ⁵	X	X	X	X	X
Vital signs ⁶	X	X	X	X	X
Pregnancy Test ⁷	X				X
Corneal endothelial cell count	X				X
Best-corrected visual acuity	X	X	X	X	X
Corneal fluorescein staining	X	X	X	X	X
Slit-lamp examination	X	X	X	X	X
Intraocular pressure measurement	X	X	X	X	X
Fundus examination	X				X
12-lead ECG examination	X				
Drug allocation ⁹	X				
Study drug administration ¹⁰	X	X	X		
Drug compliance assessment		X	X	X	
Recoding of concomitant medications	X	X	X	X	X
Adverse events ¹¹	X	X	X	X	X
Check of diary card		X	X	X	
Return of drugs				X	X

1.Demographic information: date of birth, gender, ethnicity, height, weight.

2.Medical history collection: including past medical history, surgical history, current medical history (time of onset, cause, etc.), comorbidities, medication history, etc. Any clinically significant examination results other than the research disease found during the screening period should be recorded as medical history.

3.Symptom scoring: Four symptoms (pain, foreign body sensation, photophobia, and tearing) were scored using a 3-point scale (0 = none, 1 = mild, 2 = moderate, 3 = severe). Under the guidance of the researchers, the subjects scored according to the actual situation on the day before the visit and checked in the record form.

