2.2.2 Secondary Endpoints

Clearance rate: The clearance rate of each major pathogenic bacteria at Visit 2, 3, 4 and 5: Stratified analysis shall be conducted according to the type of pathogenic bacteria and the visit time point, and the clearance rate of each kind of bacteria by the investigational drug at different times shall be calculated. Bacterial clearance is defined as positive bacterial culture at baseline and negative bacterial culture at the last visit. Bacterial clearance rate = (number of subjects cleared + number of subjects assumed to be cleared) / total number of subjects enrolled × 100%.

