6.5.3 Biological sample test indicators

Collection of conjunctival sac secretions: Collect a bacterial culture tube and sterile swab from the central laboratory before sampling, and fully expose the bulbar conjunctiva and fornical conjunctiva when sampling. Use a sterile swab moistened with sterile 0.9% sodium chloride solution to gently swab the surface of the conjunctival sac 4 times starting from the inner canthus and rotating from the inside to the outside (pay attention not to missing the inner canthus, and collect the dense secretions), avoid contact with the eyelashes and eyelid margins, and use eyelid speculum and other appliances if necessary. After sampling, put the specimens into a sterile transfer tube, mark them, and send them to the laboratory department of the hospital for bacterial culture. All subjects are required to take secretions from both eyes separately for bacterial culture, with the subject number and eye type indicated.

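### The Visit 5 procedure list in section 6.4 leaves out the conjunctival swab that the flow chart schedules and the secondary endpoint needs

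*Combined protocol and SAP*

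**What the plan says.** The flow chart in the synopsis has a row for "Collection of conjunctival sac secretion" with a mark under each of the five visits. Its last column, Visit 5/EOS, is labelled "Day 14/ Early withdrawal".

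Sections 6.1 to 6.4 turn the flow chart into procedure lists:

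- Section 6.1 (Visit 1) has "11) Collection of conjunctival sac secretion", followed by the fundus examination as item 12.
- Section 6.2 (Visits 2 and 3) has "8) Collection of conjunctival sac secretion".
- Section 6.3 (Visit 4) has the swab as item 8 too.
- Section 6.4 (Visit 5) has "8) Fundus examination" in that position. No swab or culture appears among its twelve items or in the text below them.

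The secondary endpoint (synopsis and section 2.2.2) is "The clearance rate of each major pathogenic bacteria at Visit 2, 3, 4 and 5". The second pathogen table in section 7.2.2 has a Visit 5 row.

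**The concern.** Two operative parts of the protocol tell a site different things about Visit 5. The flow chart calls for a swab and section 6.4 does not. A coordinator preparing the visit from section 6.4 would not take one, and a Day 14 culture cannot be recovered afterwards.

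At such a site, Visit 5 clearance would either be missing or be inferred from the clinical picture through the assumed categories in section 7.2.1. The endpoint at that visit would then mix culture results with clinical inference, according to which page each site used. The gap also reaches subjects who leave early, because section 6.4 directs them to the tests of the last visit where possible.

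**Working it through.** The plan gives no figure on this point to reproduce, so the check compares the passages and makes a few counts.

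**1. Flow chart against section 6.4.** The flow chart marks 14 rows at Visit 5: symptom score, clinical score, secretion, vital signs, pregnancy test, endothelial cell count, visual acuity, fluorescein staining, slit lamp, intraocular pressure, fundus, concomitant medication, adverse events and drug return. Section 6.4 covers 12 of these as list items, plus drug return in the text below: 12 + 1 = 13. Then 14 − 13 = 1, and the missing row is the secretion sample.

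**2. Could this be a reading error in the table or list?** The secretion row has five marks for five visit columns, so the Visit 5 mark cannot be a shifted one. Section 6.4 is numbered 1 to 12 without a gap, so no line has dropped out of the list.

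**3. The lists side by side.**

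| Section | Visit | Swab | Fundus examination |
|---|---|---|---|
| 6.1 | 1 | item 11 | item 12 |
| 6.2 | 2 and 3 | item 8 | not listed |
| 6.3 | 4 | item 8 | not listed |
| 6.4 | 5 | **not listed** | item 8 |

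Items 1 to 7 are the same in sections 6.2, 6.3 and 6.4. Swab visits total 5 of 5 in the flow chart and 4 of 5 in sections 6.1 to 6.4.

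**4. Does another passage supply the instruction?** Section 6.5.3 says "All subjects are required to take secretions from both eyes separately for bacterial culture", but it describes technique and names no visit. The same holds for flow-chart footnote 5. Neither one schedules a Visit 5 swab.

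**5. Which side reflects the intent?** Several places need a Visit 5 culture or presuppose one:

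- the secondary endpoint, which names Visit 5;
- the definition of clearance by the culture at the last visit, which is Visit 5 for completers;
- the replaced and re-infected categories in section 7.2.1, which rest on culture one week after treatment (last dosing day 7, and 7 + 7 = Day 14);
- the Visit 5 row in section 7.2.2;
- flow-chart footnote 8, which puts any pupil dilation for the fundus examination after the secretion sample. The fundus examination is scheduled only at Visits 1 and 5.

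**6. Size.**

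- Time points affected: 1 of 4 (Visits 2, 3, 4 and 5).
- Specimens at stake if every site followed section 6.4, before dropout: 120 subjects × 2 eyes = 240.
- Effect of one subject on an arm's rate: section 2.2.2 computes the rate as ("number of subjects cleared + number of subjects assumed to be cleared) / total number of subjects enrolled", times 100%. With 60 enrolled per arm, a subject who would have been cleared, has no culture and is not assumed cleared stays in the denominator and leaves the numerator: 1/60 = 1.67 percentage points.

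**The case against.** The strongest reply is that this is a one-line slip with no real doubt about intent. Footnote 8, the one-week categories, the endpoint and the section 7.2.2 table all agree with the flow chart. Section 11.4 has researchers trained on the same protocol, and section 10.2.2 has the eCRF built from it, so many sites would probably take the swab anyway. That is fair, and omission at every site is unlikely. It does not remove the problem, because both safeguards derive from a protocol that contradicts itself, and section 6.4 is the list a site would use to run the visit.

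A second reply concerns the direction of the error. Section 1.1 says the disease can resolve untreated within 10 to 14 days, so many subjects may be symptom-free at Day 14. If sites count them as assumed cleared, the Visit 5 rate might not fall, and it would rise if some still carried the pathogen. This stands: the net direction is not determined. The assumed-clearance rule speaks of material that cannot be obtained or sampling that is too invasive, and does not clearly cover a swab that was simply not listed. The assumed-not-cleared rule does cover clinically ineffective patients without a culture.

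Third, 1/60 is the weight of any single subject and does not measure how large the loss will be. The endpoint is also stratified by pathogen, and the plan does not say whether all enrolled subjects form the denominator for each organism. Both points are correct, so the figure should be read only as a conditional unit.

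Finally, the omission does not depend on treatment arm, no between-arm bias has been shown, and this is a preliminary Phase II study without a sample-size calculation (section 3.4). These points limit the harm but do not resolve the contradiction.

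**Conclusion.** The concern holds. Section 6.4 contradicts the flow chart and, followed literally, yields no culture at one of the four time points of the secondary endpoint. The contradiction itself is certain. The loss of data is conditional on sites working from section 6.4, and the documents do not allow an estimate of how many would.

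The 1.7-point effect per subject assumes 60 enrolled in the arm, the formula as written, and a subject who would have been cleared but is not counted as assumed cleared. Missingness could differ by site. The primary endpoint, which rests on congestion and secretion scores, is untouched. The correction should be made, because a lost swab cannot be replaced and the repair is trivial.

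**What to change.** Add the collection of conjunctival sac secretion to the section 6.4 list, immediately before the fundus examination, and renumber the items that follow. That order matches items 11 and 12 of section 6.1 and respects footnote 8. Section 6.4 then agrees with the flow chart, including its early-withdrawal column, and the swab visits in sections 6.1 to 6.4 rise from 4 to 5.

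The cost is one line of text. No visit, procedure or sample is added beyond what the flow chart already schedules. Reconciling in the other direction would mean removing Visit 5 from the flow-chart row, the secondary endpoint and the section 7.2.2 table, and revisiting the last-visit and one-week definitions. That is a much larger change, and the other passages do not support it.
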